9.3 Cost-effectiveness analysis

To compare the cost-effectiveness of each intervention compared to control, we will follow recommendations from the Second Panel on Cost-Effectiveness in Health and Medicine.^{29,30} Based on the Panel's recommendations, we will use two perspectives: a health care sector perspective and a societal perspective. Our primary analysis will use differences between each intervention and control in measures of physical activity (steps and minutes of MVPA), and in health-related quality of life measured by the EQ-5D,¹⁹⁻²¹ as the outcome measures. We will explore using a simulation model to translate changes in these measures into quality-adjusted life-years (QALYs) over a longer period.³¹⁻³⁴

The costs incurred from a health care sector perspective include costs for the Way to Health research technology platform, staff, wearable devices, data storage, and financial incentives. Outcomes will be summarized in the form of incremental cost-effectiveness ratios (ICERs) that show the difference in costs between two arms of the trial (e.g., the gamification and control arms) divided by the difference in outcome (e.g., step count). Deterministic (1-way and multi-way) and probabilistic sensitivity analyses will be conducted to determine the key drivers behind the cost-effectiveness ratios.

The additional costs incurred by a societal perspective include the time participants spend on the intervention and physical activity itself and out-of-pocket costs related to the intervention such as clothing for exercise. Participants will be surveyed at the end of the study to capture these measures. These additional costs will be captured within the ICERs.

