9.4 Process evaluation

9.5 Safety analysis

1. Abstract

Atherosclerotic cardiovascular disease (ASCVD) is the leading cause of morbidity and mortality in the United States (US). Regular physical activity has been demonstrated to reduce the risk of ASCVD and is associated with a number of other health benefits. Yet, less than 50% of adults in the US achieve enough physical activity to actually obtain these benefits. Insights from behavioral economics have been shown to both better reflect the ‘predictable irrationality’ of humans and to be effective in designing interventions that achieve sustained improvements in health behavior. Our prior work has demonstrated that interventions using financial incentives and gamification can leverage principles from behavioral economics to increase physical activity during 3-month interventions and sustain effects in 3-month follow-up periods. These findings warrant further investigation of longer-term effects. In this study, we conduct a four-arm randomized, controlled trial to evaluate the effectiveness of using behavioral economic approaches including gamification, financial incentives, or both to increase physical activity among patients with elevated risk for atherosclerotic cardiovascular disease during a 12-month intervention with a 6-month follow-up.

2. Overall objectives

The objective of this study is to use a randomized, controlled trial to test the effectiveness of using gamification, financial incentives, or both to increase physical activity among patients with elevated risk for atherosclerotic cardiovascular disease.

3. Aims

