Once baseline measures have been established, participants will be contacted to choose their goals using an approach we have found to work well in previous studies. They will be given their baseline step count and asked to select a step goal increase of 33%, 40%, 50% or choose a custom goal as long as it is at least 1500 steps greater than baseline. We have used this approach in the past because it gives participants the options of setting their own goal but also steers people to choose one of the options provided, any of which would be terrific from the standpoint of increasing physical activity. Leaving it completely open-ended risks having participants either pick goals that are ‘too easy’ or not likely to be attainable. In prior work, we find that on average participants chose ambitious goals and more than half selected a 50% step increase.

--Randomization—

Participants that have established baseline measures and finished goal selection will be randomly assigned to control or one of the three interventions using a 1:2:2:2 allocation and stratifying on baseline step count (< 4000 steps, 4000 – 7000 steps, > 7000 steps) using an electronic number generator through the Way to Health research technology platform. We do this because it preferentially increases power for comparison between the different intervention arms, as the differences between intervention arms are likely to be smaller than the difference between the intervention arms and control.

--Study Arms—

All participants will be asked to use the wearable device during the day and at night to measure activity. Each participant will primarily receive study communications by text message. Interventions by study arm will vary as follows:

--Arm 1: Control—

During the intervention and follow-up periods, participants in this arm will receive a daily text message stating whether or not they achieved their step goal on the prior day.

--Arm 2: Gamification intervention—

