4) Supportive sponsor: Each participant will select a family member or friend of their choice who will serve as a supportive sponsor. This person will receive a weekly email with the participant's progress including accumulated points, level in the game, and average step count. This supportive sponsor will help to enhance social incentives to motivate the individual towards his or her goal.³¹ We will encourage participants to select someone with whom he or she comes into frequent contact and is close to such as a partner, family member, or friend that they see often. Prior to starting in the study, we will conduct a three-way phone call with the participant and their supportive sponsor. We will provide an overview of study procedures for their arm assignment, and then prompt the participant and supportive sponsor to discuss ways in which they can help the participant meet their step goals. At least 3 goals will be decided upon during the conversation, and if needed, we will provide suggestions for supporting the participant. The goals that are decided upon will be entered into a survey by study staff, and will be included in weekly emails to the supportive sponsor. Every 8 weeks, we will reach out to the participant and supportive sponsor if the participant is stuck in lower levels of blue or bronze to determine if changes should be made to the original support goals.

5) Prize: At the end of the intervention period, participants in the platinum or gold levels will receive a trophy to recognize their achievement. While this is a nominal incentive of very low monetary value, it represents a culmination of participant effort, creates a sense of something to work towards while in the game, and conveys a sense of "status" to participants that achieve it.

During the follow-up period, participants in this arm will continue to receive a daily text message stating whether or not they achieved their step goal on the prior day.

--Arm 3: Financial incentive intervention—

Participants in this arm are informed that each week \$14 is placed in a virtual account for them. Each day the participant is informed of their step count on the prior day. If the step goal was achieved, the balance remains. Each day the goal is not achieved, the participant is informed that \$2 was taken away. We will use an 8-week ramp-up period in which daily goals are increased gradually from baseline to targets, as this was found to achieve sustained behavior change in previous work.

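### Section 9.3 commits to cost-effectiveness of each intervention against control only, so it need not show the incremental cost per unit gained of the combined arm over a single component

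*Combined protocol and SAP*

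**What the plan says.** Section 9.3 opens with its aim: "To compare the cost-effectiveness of each intervention compared to control". The outcome contrasts follow the same pattern: "Our primary analysis will use differences between each intervention and control in measures of physical activity" (steps and MVPA minutes) and in EQ-5D. The ICER is then defined more generally, as "the difference in costs between two arms of the trial (e.g., the gamification and control arms") divided by the difference in outcome. Gamification against control is the only example.

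The section says it follows the Second Panel's recommendations. The one consequence it draws from them is that "we will use two perspectives: a health care sector perspective and a societal perspective". Health care sector costs comprise "costs for the Way to Health research technology platform, staff, wearable devices, data storage, and financial incentives". Deterministic and probabilistic sensitivity analyses are planned to find what drives the ratios. No ICER between two interventions is named, and there is no mention of ordering arms by cost or of dominance.

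Elsewhere the plan gives weight to contrasts between interventions. The objective in Section 2 is to "test the effectiveness of using gamification, financial incentives, or both to increase physical activity". Section 5.1 justifies the 1:2:2:2 allocation because "it preferentially increases power for comparison between the different intervention arms". Section 9.1 powers the trial for six between-arm comparisons.

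**The concern.** A health system can offer usual feedback, gamification, incentives, or both, but only one of these to a given patient. The economic question about the combined arm is therefore what it adds, and at what extra cost, over the component that would otherwise be offered. A ratio against control averages the cheap and the expensive part of a combined programme. It can look moderate while the added component buys little, or the reverse.

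The components have different cost structures. Gamification uses staff time: before the start, "we will conduct a three-way phone call with the participant and their supportive sponsor", and every 8 weeks staff contact participants stuck in the lower levels. Incentives are cash. The combined arm has both. If only the contrasts named in 9.3 are reported, the marginal comparison and its uncertainty may be missing. Alternatively, the pairs may be picked after the results are known.

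**Working it through.** Section 9.3 gives no cost, ICER or precision figure, so there is none to reproduce. The check has four steps.

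**1. Contrasts committed to.** Four arms give 4 x 3 / 2 = 6 pairs. Section 9.1 powers six. Section 9.3 names three, all against control. The three left open are combined vs gamification, combined vs incentives, and gamification vs incentives.

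**2. What the documents fix about cost.** Section 5.1 (Arm 3) endows $14 per week and removes $2 per missed day. Taking 12 months as 52 weeks, the maximum is 14 x 52 = $728 per participant. No other unit cost is given.

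**3. Can the marginal ratio be read from the ratios against control?** Let G be the cost of gamification over control, I the incentive money kept, Ec the step gain of the combined arm over control, and Es the gain of the single component. If the same I is kept in both incentive arms:

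- combined vs control = (G + I) / Ec
- combined vs gamification = I / (Ec - Es)
- combined vs incentives = G / (Ec - Es)

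The following inputs are assumptions for illustration only: G = $100 to $400; 30% to 80% of $728 kept, so I = $218.40 to $582.40; Ec = 1000 steps. The marginal ratio divided by the combined arm's ratio against control is then:

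| Es (steps) | Combined vs gamification | Combined vs incentives |
|---|---|---|
| 500 | 0.7 to 1.7 | 0.3 to 1.3 |
| 700 | 1.2 to 2.8 | 0.5 to 2.2 |
| 800 | 1.8 to 4.3 | 0.7 to 3.2 |

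Example: gamification $100 and 800 steps; incentives $436.80 (60% kept) and 600 steps; combined $536.80 and 1000 steps.

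- Against control: 100/800 = $0.13, 436.80/600 = $0.73 and 536.80/1000 = $0.54 per daily step.
- Incentives vs gamification: $336.80 more for 200 fewer steps, so incentives alone is dominated.
- Combined vs gamification: 436.80/200 = $2.18 per daily step, about four times the $0.54.

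Opposite example: G = $400, I = $218.40, gamification gains 500 steps. The marginal ratio is 218.40/500 = $0.44, below the 618.40/1000 = $0.62 against control.

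Equal retention is a simplification. Money is kept only on days when the goal is met, so an arm that walks more would probably keep more. Each extra 10 percentage points kept in the combined arm adds $72.80 to its cost. The combined vs incentives figures would then be too low.

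**4. Precision of a contrast between interventions.** From Section 9.1: SD 2500 steps, SD 20 MVPA minutes, 300 per intervention arm, 10% dropout (270). With a simple two-sample approximation, the 95% half-width is 1.96 x SD x sqrt(2/n):

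- steps: 1.96 x 2500 x sqrt(2/300) = 400; with n = 270, 422
- MVPA: 1.96 x 20 x sqrt(2/300) = 3.2 minutes; with n = 270, 3.4

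An observed difference smaller than this has an interval that includes zero. The 200-step difference in the first example is such a case, so its $2.18 would be an unstable ratio.

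**The case against.** The strongest reply is that 9.3 already leaves room. It defines an ICER between two arms in general, and control appears only inside an example. That is correct. A reader might infer that the plan rules out comparisons between interventions, and the text does not support this. What stands is narrower: they are permitted but not required.

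Second, the plan adopts the Second Panel's recommendations, which might cover multi-arm comparison. Their text is not in the documents, so the reference can be counted neither as a commitment nor as leaving the gap open.

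Third, all contrasts share one control. If incremental costs and effects are tabulated separately, point estimates for combined vs a single component, and simple dominance, follow by subtraction. This is true and limits the loss. It does not supply the uncertainty of those contrasts, and it fails if only ratios are reported. The planned sensitivity analyses examine what drives the ratios and add no contrasts.

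Fourth, cost-effectiveness is neither in the stated objective, which concerns effectiveness, nor among the outcomes in Section 3. Section 9.1 powers six comparisons, but Section 9.2 does not list them. This supports treating the point as an improvement to a supporting analysis rather than a flaw in the trial.

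Fifth, almost all cost and effect inputs above are invented. That also stands: they show that the ratios can differ, not by how much they will.

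**Conclusion.** The point holds in limited form. As written, 9.3 commits to three contrasts against control. These do not by themselves give the incremental cost per unit gained of the combined arm over gamification or over incentives, show whether an arm is dominated, or give the uncertainty of those contrasts.

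Only the $728 maximum, the SDs, the arm sizes and the dropout rate come from the documents. The dollar-per-step figures and the overall 0.3 to 4.3 range are purely illustrative. The half-width of about 400 to 422 steps rests on Section 9.1's SD and a simple two-sample approximation.

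Two further readings are tempting but unsupported. One is that ratios against control would flatter the combined arm: the examples go both ways, and the direction is not known in advance. The other is that extra ICERs would show whether the combined arm is worth its cost. They give its marginal price and any dominance. Worth needs a value per step, MVPA minute or EQ-5D unit, which 9.3 does not set, and its QALY modelling is only exploratory.

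The primary outcome, sample size and error rate are unaffected. Label: cheap improvement.

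**What to change.** In Section 9.3, keep the ratios against control and add:

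- An incremental analysis that orders the four arms by mean cost, flags dominated arms, and reports the ICER of each remaining arm against the next less costly one.
- Incremental cost and incremental effect, reported separately, for combined vs gamification and combined vs incentives.
- Uncertainty for these contrasts from participant-level data, for example a joint bootstrap of costs and effects. Costs should use the incentive money actually kept in each arm. Where the interval for the effect difference includes zero, the cost and effect differences should be shown rather than the ratio alone.

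The cost is SAP wording and a modest amount of analysis and reporting. Applied to all three outcomes and both perspectives, it means up to 3 x 2 = 6 tables, with the bootstrap run alongside the five imputations of Section 9.2. It needs no data beyond what the plan already collects.

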8.2 Procedures

After providing informed consent, participants will complete an online questionnaire to confirm eligibility and complete the study surveys. Eligible participants will be mailed a wearable activity tracking device to wear for about two weeks to collect a baseline step count.

Participants will select step goals and then be randomly assigned as described in the Study Design section.

Surveys and interviews will be conducted as outlined in the Table:

Area	Name	# Questions	Baseline	6 Months	12 Months	18 Months	Validation Study
Screening Survey	NA		X				
Baseline (demographics)	NA		X				
Cardiovascular history/Weight/Meds	NA		X	X	X	X	
Health status	EQ-5D-5L and EQ-VAS	6	X	X	X	X	Janssen MF, Pickard AS, Golicki D, Gudex C, Niewada M, Scalone L, Swinburn P, Busschbach J. Measurement properties of the EQ-5D-5L compared to the EQ-5D-3L across eight patient groups: a multi-country study. Qual Life Res. 2013;22(7): 1717-1727.
Exercise self-efficacy	Self-Efficacy for Exercise Behaviors	12	X	X	X	X	Sallis JF, Pinski RB, Grossman RM, Patterson TL, Nader, PR. The development of self-efficacy scales for health-related diet and exercise behaviors. Health Education Research. 1998;3:283-292.
Sleep	Pittsburg Sleep Quality Assessment	9	X	X	X	X	Buysse DJ, Reynolds CF, Monk TH, Berman SR, Kupfer DJ. The Pittsburgh Sleep Quality Index: A new instrument for psychiatric practice and research. Psychiatry Research. 1989;28:193-213
Mood	PHQ9	9	X	X	X	X	Kroenke K, Spitzer RL, Williams JB. The PHQ-9: validity of a brief depression severity measure. J Gen Intern Med. 2001;16(9):606-613.
Social Support	MOS Social Support	19	X	X	X	X	Sherbourne CD, Stewart AL. The MOS social support survey. Soc Sci Med. 1991;32(6):705-714.
Risk Preferences	DOSPERT	30	X				Blais A, Weber EU. A domain-specific risk-taking (DOSPERT) scale for adult populations. Judgement and Decision Making. 2006;1(1):33-47.
Personality	Big Five	44	X				John OP, Srivastava S. The Big-Five trait taxonomy: History, measurement, and theoretical perspectives. In L. A. Pervin & O. P. John (Eds.), Handbook of personality: Theory and research. New York: Guilford Press. 1999;2: 102-138.
Grit	Grit Scale	10	X				Duckworth AL, Quinn PD. Development and validation of the short grit scale (grit-s). J Pers Assess. 2009;91(2):166-174.
Qualitative survey	NA				X	X	
Interviews						X	

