9.5 Safety analysis

Participants will be asked to report any study-related injuries or hospitalizations. These will be reviewed with the Principal Investigator and the patient will be contacted if there is a risk to continuing in the trial. We will constitute a DSMB comprised of 3 experts with one being a statistical expert, another an expert in physical activity, and a third being someone who is experienced in leading trials of behavioral interventions. As per NIH guidelines we are not naming anyone now so as not to preclude reviewers from their academic institutions. All adverse events will be reported to the IRB and DSMB. We will also ask participants to report study-related injuries, falls, emergency department visits, and hospitalization on the 12-month and 18-month surveys. We will evaluate these data in a blinded fashion after 25%, 50%, 75%, and 100% of participants complete the intervention and follow-up periods. This plan will be reviewed with the DSMB and modified as necessary prior to participant enrollment. Our plan will be to have milestone-driven meetings with the DSMB likely approximately every six months.

References

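### The cost-effectiveness ratio is labelled health care sector, but every cost listed for it is a cost of delivering the programme, and no medical care is costed anywhere in the plan

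*Combined protocol and SAP*

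**What the plan says.** Section 9.3 commits to a published standard and to two viewpoints: "we will follow recommendations from the Second Panel on Cost-Effectiveness in Health and Medicine", and "we will use two perspectives: a health care sector perspective and a societal perspective". For the health care sector viewpoint the plan says: "The costs incurred from a health care sector perspective include costs for the Way to Health research technology platform, staff, wearable devices"; the items named are, in full, "platform, staff, wearable devices, data storage, and financial incentives". For the societal viewpoint the plan says: "The additional costs incurred by a societal perspective include the time participants spend on the intervention and physical activity itself and out-of-pocket costs", the last of these being costs related to the intervention. The ratios are to "show the difference in costs between two arms of the trial", divided by the difference in outcome, with step count as the example. A simulation model is mentioned as exploratory, and only as a way of producing long-term QALYs.

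Health care use does appear elsewhere, without any link to costs:

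- Section 9.5 (safety) asks participants to "report study-related injuries, falls, emergency department visits, and hospitalization on the 12-month and 18-month surveys".
- The survey table in section 8.2 has a row headed "Cardiovascular history/Weight/Meds", completed at baseline and at 6, 12 and 18 months.
- Section 6 uses the electronic health record and the clinical data warehouse to find potentially eligible patients.

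**The concern.** A ratio presented from the health care sector's viewpoint will be read as counting what happens to health care spending. This one, as specified, counts only what it costs to run the programme.

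The plan itself gives reasons to expect effects on care use in both directions. Section 9.1 argues that more activity lowers cardiovascular risk and events, even for small increases. Sections 5.3 and 5.5 admit patients with existing ASCVD. Section 9.5 monitors injuries, falls, emergency visits and hospitalization. Neither a saving from fewer events nor an added cost from injuries could enter the numerator.

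Two other parts of section 9.3 are affected. The sensitivity analyses are meant to find what drives the ratios, but they cannot identify an input that is absent. The exploratory model could credit long-term health gains without the cost consequences that go with them.

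**Working it through.** The documents state no cost and no ratio, so there is no figure to reproduce. The check is a reading of the text, followed by one calculation on precision.

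**Step 1: classify each listed cost (section 9.3).**

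| Item | Perspective | Type |
|---|---|---|
| Technology platform | Health care sector | Programme delivery |
| Staff | Health care sector | Programme delivery |
| Wearable devices | Health care sector | Programme delivery |
| Data storage | Health care sector | Programme delivery |
| Financial incentives | Health care sector | Programme delivery |
| Participant time | Added for societal | Participant cost |
| Intervention-related out-of-pocket costs | Added for societal | Participant cost |

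Medical care items in the health care sector list: 0 of 5. In the societal additions: 0 of 2.

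**Step 2: look for medical costs elsewhere.** Sections 5.1, 6, 8.2, 9.1 and 9.5 name no unit-cost source, no costing rule for admissions, visits or medications, and no link from the safety or medication data to section 9.3. By contrast, section 9.3 does say how the societal items will be collected, by a survey at the end of the study.

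**Step 3: ask whether the data described could support a care-cost ratio.**

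- Section 9.5: the qualifier that events be study-related may govern the whole list, and the opening of that section applies it to injuries and hospitalizations. All-cause use may therefore not be captured. The survey items are self-reported at 12 and 18 months, with no stated recall window.
- Section 8.2: the medication row is not described further, so it is unknown whether dose or duration is recorded.
- Section 6: record access is described for identifying patients, not for following outcomes. Section 5.6 requires a primary care physician in the health system, but that does not place every admission there.

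The data are a starting point and would need changes before costing.

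**Step 4: precision of a care-use difference.** Inputs: 150 control and 300 per intervention arm (section 9.1). Assumption: a hospitalisation risk p of 10% to 20% in both arms; the documents give none.

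SE = √[p(1 − p)(1/150 + 1/300)], and 1/150 + 1/300 = 0.01.

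- p = 0.10: √(0.09 × 0.01) = 0.030, or 3.0 percentage points; 95% margin 1.96 × 3.0 = ±5.9 points.
- p = 0.20: √(0.16 × 0.01) = 0.040, or 4.0 percentage points; 95% margin 1.96 × 4.0 = ±7.8 points.

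This treats hospitalisation as yes or no. Variation in cost between admissions would add further noise to a cost difference.

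**The case against.** The strongest reply is that the cost list is introduced by a verb that can be read as open, and that the plan cites a standard which may itself define what the perspective must contain. That standard is not available here, so this point does not rely on it. What stands is that the text does not expressly exclude care costs. But an open list does not supply a data source, a unit cost or a costing method, and the plan supplies none. At best, the component that the label most plainly implies is left unspecified.

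A second reply is that leaving care costs out of a trial-based cost-per-step ratio is defensible, because chance would dominate them. The precision calculation supports this in part. An assumed 2-point difference in hospitalisation would be only a half to two-thirds of a standard error (2/4 to 2/3). That is a reason to report two ratios rather than replace one with the other. It is not a reason to keep a health care sector label on a programme-cost ratio.

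A reader might also infer that the missing costs would reverse the sign of the ratio. The documents do not support that. Suppose $10,000 to $20,000 per hospitalisation and a 2-point difference between arms, neither of which comes from the documents. The shift is 0.02 × 10,000 = $200 to 0.02 × 20,000 = $400 per participant. Against the incentive ceiling of 14 × 52 = $728, this leaves at least 728 − 400 = $328. The $728 applies only to the two arms with financial incentives. It falls with each missed goal, while staff and platform costs come on top. With none of these known, no statement about sign can be made in either direction.

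Nor can a reader infer that the trial already holds what it needs to cost care; step 3 of the working shows why.

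**Conclusion.** The mismatch between label and content holds on the plain text of section 9.3: all five health care sector costs are programme costs, and no section lists or costs hospital, emergency or medication use. The conclusion rests on the ordinary meaning of the label and needs no outside source.

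The effect on the ratio has no defensible size, because the documents give no care costs, event rates or programme cost totals. The only quantity offered is the standard error of 3 to 4 percentage points, which depends on the assumed 10% to 20% risk.

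This is a minor point about a secondary economic analysis. It changes what the ratio can be said to show. It does not touch the primary outcome, the sample size or the main comparisons.

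**What to change.** In section 9.3:

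1. Label the ratio built from the five listed costs as a programme (implementer) perspective.
2. Use the health care sector label only for a second ratio that adds hospitalizations, emergency visits and medications at standard unit costs. Name the unit-cost source and the time window, and report both ratios with intervals.
3. For the second ratio, word the 12- and 18-month survey items as all-cause, with recall windows that together cover months 0 to 18. State whether health record access extends to outcomes.
4. If all-cause use is not captured, report only the programme-perspective ratio.

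Relabelling needs no new data. The second ratio costs a rewording of survey items, possibly a wider permission for record access, and some costing work. Its main drawback is a wide interval, which the plan should acknowledge in advance.

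### The listed societal costs in section 9.3 omit the supportive sponsor's unpaid time, so gross societal cost is understated in arms 2 and 4 by an amount the documents do not allow one to size

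*Combined protocol and SAP*

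**What the plan says.** Section 9.3 plans cost-effectiveness comparisons of each intervention with control from two perspectives.

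- **Health care sector.** The costs "include costs for the Way to Health research technology platform, staff, wearable devices, data storage, and financial incentives".
- **Societal.** Two items are added. The first is time: "The additional costs incurred by a societal perspective include the time participants spend on the intervention and physical activity itself". The second is "out-of-pocket costs related to the intervention such as clothing for exercise".
- **Source and use.** On data collection the section says "Participants will be surveyed at the end of the study to capture these measures", and on use, "These additional costs will be captured within the ICERs".

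Section 5.1 (Arm 2, component 4) brings in another person: "Each participant will select a family member or friend of their choice who will serve as a supportive sponsor". Before the start, "we will conduct a three-way phone call with the participant and their supportive sponsor", in which staff "prompt the participant and supportive sponsor to discuss ways in which they can help the participant meet their step goals". At least three support goals come out of that call. The sponsor then gets a progress email each week. Every 8 weeks there may be a further contact to revisit the support goals, but only when the participant is in one of the two lowest game levels. No payment to the sponsor is described.

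Arm 4 combines gamification with the incentive. Its text cross-refers to arms 3 and 4, but its title makes clear that arms 2 and 3 are meant. Arms 1 and 3 have no sponsor.

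**The concern.** Three parties are on the opening call: staff, participant and sponsor. Staff time is in the health care sector list and participant time is in the societal list. The sponsor's time is in neither. A societal perspective that puts a value on participants' unpaid time gives no reason for valuing the sponsor's unpaid time at zero.

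The omission is also uneven. The sponsor is meant to raise step counts, so any effect of the sponsor enters the ICER denominator in arms 2 and 4, while the time that produced it is missing from the numerator. Control and arm 3 have no such input. The gap therefore acts in one direction on gross cost, in favour of the two arms with gamification. If the time is not collected during the trial, a later sensitivity analysis could only vary a guess.

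**Working it through.** The documents give no cost, time or ICER figure on this point, so there is no stated result to reproduce. The check has two parts.

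**1. Cost lists against arm content**

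| Input to the intervention | Arms | Where costed in 9.3 |
|---|---|---|
| Platform, staff, devices, data storage | as used | health care sector list |
| Incentive payments | 3, 4 | health care sector list |
| Participant time | all | societal list |
| Participant out-of-pocket costs | all | societal list |
| Supportive sponsor's time | 2, 4 | not named |

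Section 9.1 gives 150 participants in control and 300 in each intervention arm. Arms with a sponsor: 300 + 300 = 600 of 1,050.

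Direction: sponsor time is zero in arms 1 and 3 and cannot be negative in arms 2 and 4. Leaving it out lowers the incremental societal cost of arms 2 and 4 against control, and of arm 2 against arm 3. Between arms 2 and 4 it largely cancels.

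**2. Illustrative size**

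The number of weeks (52) follows from the 12-month intervention. Call length, weekly minutes and the hourly value of time are assumptions; none is in the documents.

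Omitted cost per participant = (call hours + weekly minutes x 52 / 60) x hourly value.

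*Wide range*, with a 0.5-hour call and $10-30 an hour:

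| Sponsor minutes per week | Hours over 52 weeks | Cost at $10-30/hour |
|---|---|---|
| 0 | 0.5 | $5-15 |
| 5 | 0.5 + 4.33 = 4.83 | $48-145 |
| 15 | 0.5 + 13 = 13.5 | $135-405 |
| 30 | 0.5 + 26 = 26.5 | $265-795 |
| 60 | 0.5 + 52 = 52.5 | $525-1,575 |

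*Specified tasks only*, assuming a 0.5-hour call, 1-2 minutes per weekly email, and zero to six 10-minute contacts (52 / 8 = 6.5, so at most six):

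- Low: 0.5 + 52 x 1/60 + 0 = 0.5 + 0.87 = 1.37 hours.
- High: 0.5 + 52 x 2/60 + 6 x 10/60 = 0.5 + 1.73 + 1.0 = 3.23 hours.
- At $20 an hour: about $27-65. At $15-30 an hour: 1.37 x 15 = about $20 to 3.23 x 30 = about $97.

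The distance between the two ranges is the informal help the support goals may generate, such as walking together. The protocol invites that help but does not quantify it.

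**The case against.** Several points on the other side have force.

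- **The list may not be closed.** Section 9.3 says the societal costs include these items, and it commits to an external guideline that cannot be consulted here. A reader might infer that the plan deliberately excludes sponsor time. The documents do not show that; they show only that it is not named. What remains is that the one source described for these costs is a survey of participants about the listed items.
- **The survey content is not shown.** The table in section 8.2 has no societal-cost questionnaire even for participant time, which section 9.3 says will be collected. Absence of a sponsor item from that table is therefore weak evidence. The fair statement is that no instrument collecting sponsor time is described.
- **The amount may be small.** This stands. The specified tasks come to a few hours over the year. Larger figures need regular weekly help that the documents do not state.
- **Ranking.** A reader might set the upper figures beside the arm 3 incentive, $14 x 52 = $728, and infer that the best-value arm could change. That is not supported. The $728 is a ceiling, reached only if the goal is met every day. No total costs or ICERs are given, and the headline comparison in section 9.3 is each intervention against control.
- **Gross is not net.** Time spent walking together may have value to the sponsor. The direction is certain for gross cost only.
- **Limited reach.** Cost-effectiveness is not among the outcomes in sections 3.1 to 3.3, and one-way, multi-way and probabilistic sensitivity analyses are already planned.

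**Conclusion.** The point holds as a cheap improvement of low severity. The listed societal costs do not name sponsor time, no described data source would capture it, and sponsors exist only in arms 2 and 4. If the plan is followed as written, gross societal cost is understated for those arms against control, and for arm 2 against arm 3.

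The documents do not fix the size. It spans about $5 to $1,575 per participant under the wide assumptions, and roughly $20-97 for the specified tasks alone. Both ranges rest on assumed minutes and an assumed hourly value. The documents support neither a claim that the understatement is large nor a claim that it changes which arm is best value. The health care sector ICERs and all step and MVPA analyses are untouched.

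**What to change.** In section 9.3:

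- Add supportive-sponsor time as a societal cost line for arms 2 and 4, valued at the same hourly rate as participant time.
- Collect it with one or two participant-reported items in the existing 6- and 12-month assessments, or in the end-of-study survey. The earlier assessments fall within or at the end of the intervention and ask for less recall. Asking participants also avoids new data collection from sponsors, for whom section 8.1 describes no consent process.
- Report time on required sponsor tasks (call, emails, 8-weekly contacts) separately from shared walking or leisure time, so that readers can include or exclude the latter.
- Vary the sponsor-time value in the sensitivity analyses already planned.
- If exclusion is intended, say so and give the reason.

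The cost is one or two survey items, one more cost line, and somewhat less favourable societal ratios for arms 2 and 4.
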